3.2. Study Outcome Measures

3.2.1. Primary Endpoints

- Incidence of BV viremia in the study population of screened renal or renal/pancreas transplant subjects.

3.2.2. Secondary endpoints

- Timing of onset of BK viremia (number of days post-transplant)

- Duration of BK viremia
- Incidence of BKVN in the study population
- Dynamics of quantitative measurements of BK viremia over time
- Frequency of donor and recipient-related risk factors for BV viremia, including:
 - a. Donor-derived factors:
 - i. Deceased donor – Standard criteria donor (SCD), Donor after cardiac death (DCD), Expanded criteria donor (ECD)
 - ii. Living donor – related donor or unrelated donor
 - iii. ABO incompatibility
 - iv. Total HLA mismatches
 - v. HLA C7 status
 - vi. Race/ethnicity
 - vii. Sex
 - b. Recipient-derived factors:
 - i. Delayed graft function (DGF), defined as use of dialysis within 7 days of the transplant
 - ii. Cold ischemia time (CIT)
 - iii. Warm ischemia time (WIT)
 - iv. Use of stents
 - v. HLA C7 status
 - vi. Type/intensity of immunosuppression, including corticosteroids
 - vii. Acute rejection
 - viii. Age
 - ix. Race/ethnicity
 - x. Sex
- Frequency of clinical outcomes that are potentially related to BKV infection, including:
 - a. subject death,
 - b. loss of graft function as defined by GFR <10 mL/min/1.73 m²
 - c. development of urinary outlet obstruction
 - d. development of gross hematuria
 - e. development of lymphocele
 - f. acute rejection
 - g. initiation of dialysis
 - h. re-transplantation
 - i. renal biopsies

3.2.3. Exploratory Endpoints

- Frequency of BK viruria (incidence, time of onset, duration, viral load quantitation by PCR) in subjects with and without BK viremia

- Frequency of CMV, EBV, HHV-6, and adenovirus viremia at multiple time points in subjects with and without BK viremia
- Frequency of CMV and adenovirus viruria at multiple time points in subjects with and without BK viremia
- Results of BK PCR assays performed on matched specimens at the participating sites (local or reference laboratories) and at the UAB Central Laboratory
- Results of urinary biomarkers of tubular injury measured at multiple time points in subjects with and without viremia, including any subjects with BKVN. Potential urinary biomarkers include cystatin C, renin, clusterin, Kim-1, b2-microglobulin, osteopontin, retinol binding protein, and markers of cell apoptosis. Urine biomarkers will not be resulted in real-time.

4. STUDY DESIGN

The primary objective is to define the natural history of BK viremia in renal or renal-pancreas transplant recipients. In order to understand the natural history of infection, we will measure the time to the development of BK viremia and its correlation with progression to end-organ disease (BKVN or BK hemorrhagic cystitis). Data from this intensive natural history monitoring period will allow for the identification of the types of high-risk patients who might benefit from future studies of therapeutic interventions for BKV infection, when effective therapy becomes available. This will be accomplished by serial quantitative BK DNA measurements by PCR in blood (plasma). It is anticipated that most samples (blood and urine) will be collected during routine standard-of-care clinic visits and will not require extra study visits. Phases of the study can be summarized as follows:

- Subject identification and informed consent. Informed consent should be obtained in the peri-transplant period (between 7 days pre-transplantation [T-7d] and 100 days post-transplantation [T+100 d]).
- Prospective screening for BK viremia. Enrollment and initiation of specimen collection should begin no sooner than 4 weeks after transplantation. Enrollment cannot occur later than 100 days after transplantation. **Subjects will be screened (collection of blood and urine for laboratory studies, including BK PCR) approximately monthly for 6 months (timed from the date of transplantation), then every other month for 6 months. For subjects who remain BKV-negative, screening will terminate approximately 12 months from the date of transplantation.**
- Intensive sampling of subjects identified with BK viremia. Subjects identified with qualifying viremia will be sampled approximately every two weeks until resolution of viremia (defined as PCR negative, or <1000 copies).
Note: Patients who did not participate in the prospective screening phase but are identified with BK viremia by standard-of-care testing may be enrolled, as long as they are still within 90 days of transplantation.
- Post-viremia follow-up. Following resolution of viremia, subjects will be sampled (collection of blood and urine) approximately monthly for 6 months (unless another termination event occurs sooner).

4.1. Informed Consent and Enrollment

In an effort to capture subjects early in the course of the evolving BK infection and to avoid subjects who have already developed evidence of BKV-induced nephropathy (BKVN), this protocol will emphasize the natural history of early-onset BK viremia. Obtaining informed consent early in the peri-transplant period is encouraged, although enrollment and study-related specimen collections will not begin until ≥ 4 weeks post-transplant. The consent form will secure the subject's informed consent to participate in the screening phase as well as the intensive monitoring phase (if qualifying viremia is subsequently identified).

Consented subjects can be enrolled as early as 4 weeks and as late as 100 days following renal/renal-pancreas transplant surgery. The 4-week delay prior to enrollment and initiation of specimen collection will allow post-transplantation stabilization of renal function, immunosuppressive dosing, and other clinical parameters.

4.2. Prospective Screening Phase

Approximately 450 subjects will be screened for BK viremia (15% over-enrollment allowed, to a maximum of 518 screened subjects). During the screening phase, subjects will submit blood (plasma) for quantitative measurement of BKV DNA approximately every 4 weeks, ± 7 days, for 6 months (timed from the date of transplantation) and then approximately every 8 weeks, ± 14 days for 6 months. Also, urine specimens will be collected at each visit and stored for subsequent testing. During the screening phase, the specified intervals between sample collections should be followed as closely as possible, but may vary with subject availability. If qualifying BK viremia is not detected, surveillance will terminate approximately 12 months after the date of transplantation (or when another study termination endpoint is reached, whichever occurs sooner).

NOTE: BKV PCR results of $\geq 10,000$ from the study central laboratory, the site laboratory, or a reference laboratory are acceptable to qualify the patient for inclusion in the Intensive Monitoring Phase of the study.

NOTE: Non-study patients who are determined to have a qualifying blood BK viral load ($\geq 10,000$ copies/ml) during the course of routine clinical care (i.e., patients not consented and not identified by prospective screening/surveillance) will also be eligible for enrollment directly into the intensive monitoring surveillance phase after providing consent as long as they remain within the window of ≤ 100 days following transplantation.

Subjects will remain in the screening/surveillance phase: 1) for 12 months post-transplantation; 2) until qualifying BK viremia is documented; 3) until renal graft failure, re-transplantation, and/or initiation of chronic dialysis occurs; 4) death; 5) until subject decides to terminate participation; 6) until the investigator decides that the subject should terminate participation; or 7) until the study closes (whichever occurs first). Reason for termination of participation in the study will be documented.

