5. STUDY POPULATION

5.1. Study Population Selection

All adult renal or renal-pancreas transplant patients who meet protocol inclusion/exclusion criteria are eligible for participation in this study.

In an effort to capture subjects early in the course of the evolving BK infection and avoid subjects who have already developed evidence of BKVN, this protocol will emphasize consent in the early peri-transplant period. Patients may be consented while hospitalized pre-transplantation (as early as 7 days prior to transplantation) or at an outpatient follow-up visit (as late as 100 days post-transplantation). The study enrollment visit and initial collection of protocol-defined specimens will take place between 4 weeks and 100 days following renal or renal/pancreas transplantation.

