8.4.1. Primary Outcome Analysis

Incidence of BK viremia will be estimated using a 95% confidence interval for single proportion. Logistic regression will be used to investigate the risk factors for BKV viremia and BKVN. Factors will include:

- Donor-derived factors:
 1. Deceased donor – Standard criteria donor (SCD), Donor after cardiac death (DCD), Expanded criteria donor (ECD)
 2. Living donor – related donor or unrelated donor
 3. ABO incompatibility
 4. Total HLA mismatches
 5. HLA C7 status
 6. Race/ethnicity
 7. Sex
- Recipient-derived factors:
 1. Delayed graft function (DGF), defined as use of dialysis within 7 days of the transplant
 2. Cold ischemia time (CIT)
 3. Warm ischemia time (WIT)
 4. Use of stents
 5. HLA C7 status
 6. Type/intensity of immunosuppression, including corticosteroids
 7. Acute rejection
 8. Age
 9. Race/ethnicity
 10. Sex

To compare the change in GFR over time between those with and without BKV viremia, we use all available GFR data from each subject. We will use mixed model for repeated measures to analyze the GFR data over time. This analysis method will allow us to use any of the available GFR data

even if they are not complete. We will determine the appropriate covariance structure to use as indicated by the Akaike Information Criterion.

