8.4.2. Secondary Endpoints

The distribution of the time to onset and duration of BKV viremia will be estimated using survival analysis methods such as Kaplan-Meier estimator for a single group. This will provide estimates of the median time to onset or median duration of BKV viremia. To compare different groups and/or determine risk factors, we will use Cox proportional hazard regression model if the proportional hazards assumption is found to be reasonable. Otherwise, we will consider using parametric survival regression models (in particular, accelerated failure time model). Parametric regression models are useful especially in cases where sample sizes are small or when the percent censored is high. This will also be the tool of preference if there will be left-censored subjects, i.e., subjects who at enrollment show evidence of BK viremia. Cox model cannot handle left-censored data.

As with the BKV viremia, incidence of BKVN will be estimated using a 95% confidence interval for single proportion. We will utilize logistic regression to compare groups, or adjust for covariates or determine risk factor.

To investigate the change in the quantitative BK viremia over time and how it is associated with important factors such as the use of immunosuppressive therapy and recipient's demographic and clinical characteristics, we will again use mixed regression modeling for repeated measures.

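### Section 8.4 names no analysis set, so patients enrolled because they are already viremic could be pooled into the incidence and onset estimates

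*Combined protocol and SAP*

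**What the plan says.** **The entry route.** Section 4.2 describes people found to have at least 10,000 copies/ml in routine care, "patients not consented and not identified by prospective screening/surveillance", who "will also be eligible for enrollment directly into the intensive monitoring surveillance phase after providing consent". The Protocol Summary and section 4 repeat this route. The window differs: section 4.2 allows it "as long as they remain within the window of" 100 days from transplant and the Protocol Summary also gives 100 days, but section 4 says "as long as they are still within 90 days of transplantation".

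**The endpoint and the target.** Section 3.2.1 defines the one primary endpoint as "Incidence of BV viremia in the study population of screened renal or renal/pancreas transplant subjects". Section 8.2.1 counts the target of about 40 viremic subjects (maximum 60) from those enrolled in the screening group. Section 3.2.2 lists BKVN incidence in the study population, without the word *screened*.

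**The analyses.** Section 8.4.1 says "Incidence of BK viremia will be estimated using a 95% confidence interval for single proportion" and gives no denominator; the logistic models for viremia and BKVN have no stated analysis set either. Section 8.4.2 says "The distribution of the time to onset and duration of BKV viremia will be estimated using survival analysis methods", and prefers parametric models if some subjects are viremic at enrolment, whom it calls left-censored.

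**Ordinary entry.** Under section 5.1, consent may be given "at an outpatient follow-up visit (as late as 100 days post-transplantation"). Section 5.3.2 excludes only BKVN and chronic dialysis after graft failure. Item 9 of section 6.1 records a routine BK PCR result at the Enrollment Visit.

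**The concern.** A direct enrollee is recruited because the outcome has already happened. The routine-care patients who tested negative alongside that person are not enrolled in step. Each one therefore adds 1 to both numerator and denominator of a proportion, and each has an onset no later than the end of the entry window.

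If these subjects were analysed with the screened cohort, incidence would be too high, onset would look too early, and the size of both effects would depend on how much routine BK testing each site does before consent. Incidence is the only primary endpoint, and time to onset is part of the first primary objective. With no analysis set in section 8.4, the choice would be made after the data are seen.

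**Working it through.** **1. The plan's own figure.** Section 8.2.1 states at least 90% probability of finding 40 or more viremic subjects among 450 if the true proportion is 11%. The exact binomial tail P(X ≥ 40 | n = 450, p = 0.11) is 0.938, so the statement holds. The calculation treats every viremic subject as one of the 450; direct enrollees have no place in it.

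**2. Inputs for the pooling check.** From section 8.2.1: 450 screened and a worked-example proportion of 10%, hence 45 cases. From section 4.3: at most 60 viremic subjects. The number D of direct enrollees is not given, so it is an assumption. If all screened cases count toward the cap, D is at most 60 − 45 = 15.

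**3. Incidence if pooled.** The estimate is (45 + D)/(450 + D), with exact (Clopper-Pearson) intervals. Coverage is the probability that the interval from the pooled data contains the true 10% when the screened count is binomial(450, 0.10).

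| D | Estimate | 95% CI | Coverage of 10% |
|---|---|---|---|
| 0 | 45/450 = 10.0% | 7.4–13.2% | 96% |
| 5 | 50/455 = 11.0% | 8.3–14.2% | 91% |
| 10 | 55/460 = 12.0% | 9.1–15.3% | 76% |
| 15 | 60/465 = 12.9% | 9.99–16.3% | 54% |

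Starting from 40/450 = 8.9%, the cap allows D = 20. This gives 60/470 = 12.8% (9.9–16.1%), with coverage of 8.9% about 18%.

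**4. Onset if pooled.** Assume 40% of the 45 screened cases occur by day 100, that is 18. Ten direct enrollees raise the share of cases with onset by day 100 from 18/45 = 40% to 28/55 = 51%, and naive day-100 incidence from 18/450 = 4.0% to 28/460 = 6.1%. For early shares of 30% to 60%, day-100 incidence goes from 3.0–6.0% to 5.1–8.0%. Left-censoring says only that onset preceded enrolment. It does not undo the fact that the subject was enrolled because of it.

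**5. Risk factors.** Assume a true odds ratio of 2.0, 30% exposed and 10% incidence. The expected table is 19.9 exposed cases, 115.1 exposed non-cases, 25.1 unexposed cases and 289.9 unexposed non-cases; 44% of cases are exposed. Adding 10 direct enrollees with the same 44% leaves the odds ratio at 2.00. If their exposed share is 20 points higher or lower, it becomes 2.32 or 1.72. Selection on outcome alone shifts the intercept, not the odds ratio.

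**6. Why exclusion alone is not a repair.** Suppose everyone with a qualifying result before entry is dropped and a simple proportion is kept. Assume 10% true incidence, 40% of it spread evenly over days 0–100, entry spread evenly over days 28–100 (mean 64), and every early case known. The fraction lost is 0.04 × 64/100 = 2.56%, so the estimate is (10 − 2.56)/(100 − 2.56) = 7.6%. The bias is now downward.

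**The case against.** The best reply is that the plan already separates these people. Section 4.2 describes them as not identified by prospective screening and sends them straight to the intensive phase. Section 3.2.1 defines incidence among screened subjects, and section 8.2.1 ties the viremic count to the screening group. A reader might infer from the entry route that the primary incidence estimate is already biased, or that direct enrollees belong to the screened cohort. The documents do not say so, and read literally these sections keep them out. That part of the objection stands.

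It does not reach the rest. The word *screened* governs one endpoint; BKVN incidence, onset and the risk-factor models have no such limit. Section 8.2.1 justifies a sample size and is not an analysis rule. Section 8.4.2 expects subjects viremic at enrolment in the onset analysis. Nor do the eligibility criteria bar a patient with a known qualifying result from an ordinary Enrollment Visit, although the separate route makes this less likely.

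Two other strong readings fail. One is that pooling would push the interval clear of the true 10%. From 45 screened cases that needs D = 20, hence 65 viremic subjects, above the cap of 60; at D = 15 the interval still includes 10%. The other is that odds ratios are necessarily biased. They are biased only if routine testing or consent depends on a risk factor, or if early-onset cases have a different risk profile.

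It is also fair that routine PCR results are already recorded, and that note 1 of Appendix A-2 distinguishes subjects consented during surveillance, so entry route can probably be recovered. That makes the repair easier. It does not define the analysis set.

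**Conclusion.** The concern holds as a gap in the analysis plan whose consequence is conditional. The protocol has an outcome-dependent entry route, and section 8.4 separates it from no analysis. For primary incidence the literal reading protects the estimate, and the plan needs only to say so where the analysis is specified. For onset and BKVN incidence the current wording would let direct enrollees in, and left-censoring does not repair that.

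If pooled, 5 to 15 direct enrollees would raise a 10.0% incidence to between 11.0% and 12.9% and cut interval coverage to between 91% and 54%. These figures rest on an assumed number of direct enrollees, 45 screened cases in 450, and the cap of 60. The onset figures rest further on an assumed share of early cases. The entry window, 100 days in two places and 90 in another, must be reconciled.

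**What to change.** In sections 8.4.1 and 8.4.2:

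- Restrict incidence of viremia and of BKVN, time to onset, and the viremia risk-factor models to subjects who entered through prospective screening without a known qualifying result.
- Because entry runs from 4 weeks to 100 days, estimate cumulative incidence and onset with delayed entry: time scale days from transplant, left truncation at enrolment. State that the result is conditional on being free of known qualifying viremia at entry.
- Give a sensitivity analysis that adds back subjects viremic at or before enrolment. This covers those first found on the enrolment sample itself, who contribute no time at risk under left truncation.
- Use direct enrollees only for duration, viral-load dynamics and post-viremia course.
- State whether the target of 40 to 60 viremic subjects includes direct enrollees.

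On the eCRF, record the entry route and the dates and results of any BKV PCR before consent. Reconcile the 90-day and 100-day windows.

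The cost is SAP wording and a few eCRF fields, with no added visits or samples. Incidence and onset will rest on slightly fewer viremic cases and have somewhat wider intervals.

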4.3. Intensive Sampling Phase

Approximately 40 viremic subjects (up to a maximum of 60) will be asked to participate in more intensive sampling. Those subjects in whom BK viremia is identified (by PCR result demonstrating BK DNA $\geq 10,000$ copies/ml) will be shifted to a more intensive sampling schedule. A review of the informed consent will be initiated by the research staff to confirm the subject's continued willingness and ability to participate in the intensive monitoring phase until resolution of viremia or until another discontinuation event occurs.

Blood and urine specimen collection will occur every 2 weeks, \pm 7 days, until the BK viremia has resolved (or another study termination endpoint is reached). Resolution of BK viremia is defined as PCR becoming negative (or viral load <1000 copies/ml). Start and stop dates for the Intensive Sampling Phase will be defined by the date that the qualifying (initial positive and subsequent negative) blood samples were drawn.

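### Section 8.4.2 provides for left censoring at enrollment but not for interval censoring of viremia onset and clearance between visits, and no dating rule is given for either endpoint.

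*Combined protocol and SAP*

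**What the plan says.** Section 3.1.1 puts time to onset and duration of viremia in the first primary objective. Section 3.2.2 lists both as secondary endpoints, onset in days after transplantation and "Duration of BK viremia" with no further definition. Neither entry says which date counts as the start or the end.

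Section 4.2 sets screening as "quantitative measurement of BKV DNA approximately every 4 weeks" (window 7 days either side) for six months from transplantation, "then approximately every 8 weeks" (window 14 days either side). Section 4.3 moves subjects with at least 10,000 copies/ml to sampling every 2 weeks (window 7 days either side) until PCR is negative or below 1,000 copies/ml. It adds that the beginning and end of this intensive phase "will be defined by the date that the qualifying (initial positive and subsequent negative) blood samples were drawn". That sentence concerns the sampling phase, not the endpoints.

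Section 8.4.2 names Kaplan-Meier as an example of the survival methods for both endpoints: "This will provide estimates of the median time to onset or median duration of BKV viremia". For comparing groups and finding risk factors it plans Cox regression, or parametric models (accelerated failure time in particular) if proportional hazards is not reasonable. It prefers parametric models where subjects are already viremic at enrollment, because Cox regression cannot handle left-censored data. It does not mention interval censoring.

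**The concern.** A subject who is negative at one screening draw and qualifies at the next became viremic at an unknown time between the two. Clearance likewise falls somewhere between two intensive draws. Ordinary Kaplan-Meier and Cox analyses of draw dates treat those dates as exact event times. Onset is then always recorded late. For any episode longer than the screening gap, the start is on average moved later by more than the end, so duration is recorded short, and by an amount that changes when the schedule changes at Month 6.

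The plan accepts this logic for the first visit, where it calls positive subjects left-censored, but does not carry it to later visits. It also does not say how duration is measured when the start precedes the first sample. Such subjects are to be expected: first sampling falls between 4 weeks and 100 days after transplantation, and patients already viremic may enter intensive monitoring directly. At stake are the descriptive estimates of onset and duration. The incidence proportion does not depend on these dates.

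**Working it through.** The documents give no precision or bias figure for onset or duration, so there is no stated figure to reproduce.

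**Inputs from the documents.** Screening gap 28 days to Month 6 and 56 days after (Section 4.2); intensive gap 14 days (Section 4.3). With both neighbouring windows used in full, gaps can reach 28 + 14 = 42, 56 + 28 = 84 and 14 + 14 = 28 days.

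**Assumptions.** Onset is uniform within its gap. No duration distribution is given, so gamma durations with medians of 42, 70, 112 and 180 days are assumed, with shape 1 (exponential), 2 or 4.

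**Step 1, onset.** Mean lag = gap/2: 28/2 = 14 days and 56/2 = 28 days. These values hold for episodes long enough not to be missed. If 50% to 90% of onsets fall in the 4-week period (assumed), the overall mean lag runs from 0.5 × 14 + 0.5 × 28 = 21 days to 0.9 × 14 + 0.1 × 28 = 15.4 days.

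**Step 2, duration within a subject.** Clearance is dated late by about 14/2 = 7 days. For an episode longer than the screening gap, the net error is 7 − gap/2: 7 − 14 = −7 days (4-week) and 7 − 28 = −21 days (8-week).

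**Step 3, allowing for missed episodes.** An episode that ends before the next screening draw is never seen. Simulating 1,000,000 episodes per setting, with a lag uniform on the gap, detection if the duration exceeds the lag, and recorded duration rounded up to the next 14-day draw, gives for shape 2, in days:

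| True median | Error within subject, 4-week | Error within subject, 8-week | Mean recorded, 4-week | Mean recorded, 8-week | Difference |
|---|---|---|---|---|---|
| 42 | −5.9 | −15.8 | 49.4 | 46.8 | 2.6 |
| 70 | −6.5 | −18.5 | 80.9 | 76.3 | 4.6 |
| 112 | −6.8 | −19.8 | 129.5 | 122.8 | 6.7 |
| 180 | −6.9 | −20.5 | 209.6 | 200.7 | 8.9 |

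Over all three shapes, the within-subject error is −5.7 to −7.0 days (4-week) and −15.4 to −20.9 days (8-week). The difference between groups in mean recorded duration is under 1 day for shape 1 and 4.2 to 12.9 days for shape 4.

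**Step 4, why the two columns of errors cannot simply be subtracted.** The 8-week schedule misses more short episodes, so those it detects are truly longer. At a 70-day median (shape 2), the true mean duration among detected subjects is about 87 days on the 4-week schedule and 95 on the 8-week schedule. Late dating pulls the recorded means to 81 and 76. Recovering true durations among detected subjects, with no allowance for missed episodes, would leave a gap of about 7 days in the opposite direction, larger than the 5 days under draw dating.

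**The case against.** Five points can be made for the plan.

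- The Section 4.3 sentence dates a sampling phase. A reader might infer that the plan fixes endpoint dates at the draws and analyses them as exact. The documents do not say so; Kaplan-Meier is offered only as an example. This stands, and the conclusion is worded conditionally. However, no other dating rule is given, which is itself a gap.
- A reader might infer that subjects viremic at entry are overlooked. They are not: Section 8.4.2 addresses their onset through parametric models. Their duration remains unaddressed.
- A reader might subtract the within-subject errors and announce a false early-late difference in duration of 10 to 14 days. A comparison of groups sees recorded durations, and missed short episodes offset part or all of the late dating. Nor should much be made of observed medians. With a true median of 70 days (shape 2) the 8-week schedule gives 56 and the 4-week schedule 70, but recorded values fall on a 14-day grid, and at true medians of 42 and 180 days the two schedules give identical medians.
- Section 8.4 plans no early-versus-late comparison; it speaks only of different groups.
- Section 2.1.1 expects most viremia in the first six months, and site or reference laboratory results may qualify a subject and so shorten a gap. The 8-week error therefore affects a minority. The lag of about 14 days remains for subjects found on the 4-week schedule.

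**Conclusion.** The concern holds for onset, and in a limited form for duration. If draw dates are used, onset is late by about 14 days on the 4-week schedule and 28 days on the 8-week schedule. This rests on uniform onset within the gap and on episodes long enough to be detected. Recorded duration is short within a subject by roughly 6 to 7 and 16 to 20 days, for assumed median durations of 42 to 180 days.

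The documents do not support a single figure for bias between early- and late-onset groups. Under the distributions tried it is about 0 days (exponential), 3 to 9 days (shape 2) or 4 to 13 days (shape 4), and the true distribution is unknown. Modelling the intervals does not by itself remove this difference, because episodes missed between visits stay missed.

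**What to change.** In Section 8.4.2:

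1. **Dating rule.** Define onset as lying after the last negative draw and at or before the first qualifying draw, and state how a detectable result under 10,000 copies/ml is classed. Treat subjects positive at their first sample as left-censored, as the section already intends.
2. **Onset analysis.** Use the Turnbull estimator, or interval-censored parametric (accelerated failure time) regression, in place of Kaplan-Meier and Cox on draw dates. This extends models the section already names.
3. **Duration.** Record both intervals: last negative to first qualifying draw, and last unresolved to first resolved draw. Report, as a sensitivity analysis, an estimate that allows for the interval-censored start and end. With about 40 viremic subjects and no correction for missed episodes, this should not be the sole analysis.
4. **Viremic at entry.** Show their durations separately, because the start is unknown.
5. **Limits.** State that episodes missed between visits are not recovered, and that any early-versus-late comparison of duration needs caution.

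The cost is a little more analysis work and slightly wider intervals. The planned schedule already yields the draw dates, so no extra samples or visits are needed.

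### Duration of viremia is likely to be overstated if patients entered directly on a routine-care result count as at risk from a blood draw that precedes their consent

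*Combined protocol and SAP*

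**What the plan says.** Section 4.2 (Prospective Screening Phase) opens a second route into the intensive phase, for non-study patients found in routine care to have at least 10,000 copies/ml. It describes them as "patients not consented and not identified by prospective screening/surveillance". The route stays open until 100 days after transplantation, and the section says that these patients "will also be eligible for enrollment directly into the intensive monitoring surveillance phase after providing consent". Their qualifying draw therefore comes before consent.

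Section 4.3 (Intensive Sampling Phase) says that the start and stop dates of that phase "will be defined by the date that the qualifying (initial positive and subsequent negative) blood samples were drawn". The ending event is also defined there: "Resolution of BK viremia is defined as PCR becoming negative (or viral load <1000 copies/ml").

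Section 3.2.2 lists "Duration of BK viremia" as a secondary endpoint without a time origin. Section 3.1.1 names duration within the first primary objective.

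Section 8.4.2 (Secondary Endpoints) states: "The distribution of the time to onset and duration of BKV viremia will be estimated using survival analysis methods such as Kaplan-Meier estimator". The estimate is a single-group one, with Cox or accelerated failure time (AFT) models for comparisons. The section prefers parametric models "if there will be left-censored subjects, i.e., subjects who at enrollment show evidence of BK viremia". It does not mention delayed entry or separate handling of direct entrants.

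**The concern.** A direct entrant comes under study observation only at consent and enrollment. If the episode is dated from the earlier routine draw, the days between draw and consent enter the analysis as time at risk. Clearance in those days would rarely be recorded. A patient known to have cleared has little reason to be entered into two-weekly sampling that runs until resolution, and outside PCR results reach the eCRF only for people who are enrolled. This is left truncation: short episodes drop out of the sample, while the survivors' pre-entry time stays in the denominator.

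At stake are the Kaplan-Meier curve and median for duration, and any Cox or AFT comparison by a factor linked to direct entry. Onset timing is the clearest such factor, because direct entry is possible only early after transplantation (100 days in the Protocol Summary and section 4.2, 90 days in the introduction to section 4; these need to be reconciled).

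**Working it through.** **Plan's own figure.** The documents give no expected duration and no precision for it, so there is nothing to reproduce.

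**Inputs from the documents.** 450 screened; 11% viremic as the rate at which the target of 40 is reached with at least 90% probability (section 8.2.1); target about 40 viremic subjects, maximum 60 (sections 4.3 and 8.2.1).

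**Inputs assumed.** Direct-entry share f = 10-50%; lag from qualifying draw to entry L = 14, 28 or 42 days; true median 60 days; durations exponential (shape k = 1) or Weibull (k = 1.5); direct entrants are enrolled only if still viremic at entry.

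**A share suggested by the plan's figures.** 450 × 0.11 = 49.5, about 50 viremic subjects from screening. Under the maximum of 60 that leaves about 10 direct entrants, and 10/60 = 17%. A lower screening yield would leave room for more.

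**Formula.** Let S be the true survival function of duration. Prospectively detected subjects follow S(t). Direct entrants, conditional on being viremic at L, follow S(t)/S(L) for t > L. With everyone at risk from the draw, the Kaplan-Meier median solves

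(1 − f)·S(t) + f·S(t)/S(L) = 0.5.

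With S(t) = 2^(−(t/60)^k) and q = 1 − f + f/S(L), this gives t = 60·(1 + log2 q)^(1/k).

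**Worked example.** k = 1, f = 0.25, L = 14: S(14) = 2^(−14/60) = 0.8507; q = 0.75 + 0.25/0.8507 = 1.0439; t = 60 × (1 + log2 1.0439) = 63.7 days, an excess of 3.7 days.

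**Excess in the median over 60 days:**

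| Share direct | Exponential, L = 14 / 28 / 42 | Weibull 1.5, L = 14 / 28 / 42 |
|---|---|---|
| 10% | 1.5 / 3.2 / 5.2 | 0.5 / 1.4 / 2.8 |
| 17% (10/60) | 2.5 / 5.3 / 8.6 | 0.8 / 2.3 / 4.5 |
| 25% | 3.7 / 7.9 / 12.6 | 1.2 / 3.4 / 6.6 |
| 50% | 7.3 / 15.1 / 23.5 | 2.3 / 6.6 / 12.3 |

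**Sampling error for comparison.** For an exponential with 40 events, the standard error of the Kaplan-Meier median is median/(ln 2 × √40) = 0.23 × median, or about 14 days at a median of 60.

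**Does delayed entry remove the bias?** A simulation of 60,000 subjects per scenario used shares of 10-50%, uniform lags with mean 7, 14 or 28 days, true medians of 45, 90 or 150 days, and shapes 1 and 1.5. Ordinary Kaplan-Meier medians were too long by about 0 to 14 days (0-32%). With entry to the risk set at consent they were 44.6-45.3, 89.5-90.4 and 148.9-151.7 days, that is, the true values within simulation error.

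**The case against.** Four objections deserve an answer.

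**The clock is an inference.** Section 4.3 dates a study phase, and section 8.4.2 names Kaplan-Meier only as an example and never says that everyone is at risk from day 0. This stands in part: a reader might infer that the plan prescribes a biased estimator, and it does not. But no other origin is given, the phase dates are the natural one, and nothing in the plan would lead an analyst to delayed entry.

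**No criterion requires viremia at consent.** This is correct. A reader might infer that the draw-to-consent interval is certain to be viremic; the documents do not support that. Section 4.2 asks for a qualifying load, consent and the time window, and a patient who had cleared could in principle enter and go to post-viremia follow-up. If all such patients were enrolled with their clearing result recorded, the bias would vanish. Nothing requires this, so the interval is largely, not wholly, event-free.

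**Subjects who had already consented.** A reader might extend the point to a consented subject whose qualifying local result predates the enrollment visit. That does not follow. Consent is possible from 7 days before transplantation, and entry to screening does not depend on viremia, so a subject who clears before that visit still enrolls.

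**The size may be small.** Section 8.2.1 expects the viremic subjects to come from screening. The 24-day figure needs half the cohort to be direct entrants, a 42-day lag for each, and exponential durations. This stands as to size. It does not affect direction, and neither a larger sample nor the reported confidence interval accounts for a one-sided bias.

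The left-censoring sentence in section 8.4.2 is no remedy. It concerns subjects already viremic at enrollment, that is, time to onset; the problem here is truncation of time to clearance.

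**Conclusion.** The point holds for patients entered directly on a pre-consent routine-care result, and for the duration endpoint only. If duration is timed from the qualifying draw and these patients count as at risk from that day, ordinary Kaplan-Meier is biased toward longer viremia. This rests on two inferences: that the section 4.3 dates serve as the duration clock, and that patients who clear before consent are mostly not entered.

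The size cannot be determined from the documents. Over the whole assumed range it is 0.5 to 23.5 days on a 60-day median. At the share that the plan's own figures suggest (17%) and a 14-28 day lag, it is 0.8 to 5.3 days, against a standard error of about 14 days. A large distortion should not be inferred. Duration is also not the primary endpoint: section 3.2.1 lists incidence alone, although duration is named in the first primary objective. The case for changing the plan is that the bias is systematic and cheap to remove.

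**What to change.** Add to section 8.4.2, in substance:

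- Duration of viremia is measured from the draw date of the qualifying sample.
- Subjects enrolled directly into the intensive phase on a routine-care result drawn before consent join the risk set at their consent/enrollment date (delayed entry, left truncation) in the Kaplan-Meier, Cox and AFT analyses.
- Subjects who had already consented when the qualifying sample was drawn are at risk from the draw; delayed entry is not applied to them.
- The estimate in prospectively screened subjects alone is reported as a sensitivity analysis.

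The cost is a few sentences and one extra analysis. The dates should already be available: Appendix A-2 note 1a covers local and central PCR collection dates, and section 6.1 defines the enrollment visit as Day 1. The statistical price is slightly fewer subjects at risk in the early part of the curve. Delayed entry assumes that a direct entrant is still viremic on joining the risk set; the screened-only analysis does not need that assumption.
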